2.1. Study Rationale

The results from Phase 2 (buttock and thigh) and Phase 3 (buttock) studies show CCH 0.84 mg given per treatment area (1 buttock or 1 thigh) is an effective treatment for edematous fibrosclerotic panniculopathy (EFP, commonly known as cellulite) based on improvement in the severity of cellulite as determined by the Investigator and the subject. There were no safety concerns following 3 doses of 0.84 mg of CCH per treatment area. The majority of adverse events (AEs) occurred at the site of injection and resolved before the next scheduled treatment in these studies. The immunogenicity profile of CCH has been consistent across all studies.

The efficacy of CCH treatment on cellulite has been demonstrated in previous clinical studies using validated photonumeric scales. This study will capture the change from baseline after CCH treatment using the validated photonumeric scales and explore tissue level changes in the treatment areas (buttocks and thigh), both from histopathology and radiology perspectives.

COVID-19 Public Health Emergency Impact

The COVID-19 public health emergency has disrupted the conduct of clinical research throughout the world. At Endo Pharmaceuticals Inc. (Endo) ensuring the safety of clinical study participants is our primary concern. In addition, the integrity of data obtained from clinical trials must be ensured.

Endo initiated study EN3835-212 at a single investigational site in November of 2019. The first subject was dosed with CCH on 26 December 2019. On 18 March 2020, the investigational site suspended Study EN3835-212 due to the COVID-19 public health emergency. At that time, 7 subjects had received at least 1 dose of CCH in this study. Of those 7 subjects, 2 had completed the 3 doses required for the study and 1 subject had completed 2 doses. No subjects had completed all assessments required for the Day 71 Visit or beyond.

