4. STUDY DESIGN

4.1. Overall Design

This is a single-center, open-label, Phase 2a study to assess the safety and efficacy of CCH in adult women with moderate or severe EFP of the buttocks or thighs using photonumeric scales, MRI, and histopathology of tissues from the treated area. Approximately 19 subjects will be dosed in this study.

This study was suspended due to the COVID-19 public health emergency on 18 March 2020. When the study re-opens, subjects who had received less than 3 doses of CCH prior to 18 March 2020 will be allowed to continue in the study and may receive any remaining doses with Sponsor approval. These subjects will complete all remaining visits and assessments EXCEPT biopsies and biopsy follow-up visits, if willing to do so. These subjects will be included in the safety assessments for the study, but will not be included in the efficacy assessments. Subjects who received less than 3 doses prior to 18 March 2020 may elect to remain in the study without receiving additional doses.

Subjects who received all 3 doses of CCH prior to 18 March 2020, will be allowed to continue in the study and complete all remaining visits and assessments (including biopsies and biopsy follow-up visits), if willing to do so. These subjects will be included in the safety assessments for the study, but will not be included in the efficacy assessments. Subjects who received all 3 doses of CCH prior to 18 March 2020 may elect to remain in the study without completing the biopsies and biopsy follow-up visits.

An additional 12 subjects will be dosed in the study. These subjects will be included in the safety assessments, and all efficacy assessments will be based on the data from these 12 subjects. For the 12 subjects who receive their first dose of study drug after 18 March 2020, every attempt will be made to enroll an equal number of subjects across the 2 severity levels in both buttocks and thighs (eg, 3 subjects with moderate buttock cellulite, 3 subjects with severe buttock cellulite, 3 subjects with moderate thigh cellulite, and 3 subjects with severe thigh cellulite).

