9.2. Populations for Analysis

For the purposes of analysis, the following populations are defined:

- The Safety Population will include all subjects who have undergone the first (screening) biopsy.
- The Evaluable Population will include all subjects in the Safety Population who received their first dose of CCH in this study after 18 March 2020 and who had a baseline and at least 1 postinjection PR-PCSS evaluation.

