4.2. Protocol Deviations

Potential deviations will be identified and documented prior to database lock. Protocol deviations will be derived from the eCRF data, electronic vendor data, and will be obtained from the clinical monitoring reports. All deviations from these sources will be reconciled and duplicate deviations will be removed.

Possible deviations include, but are not restricted to the following deviation types:

- Ineligible subject/study entry criteria not satisfied.
- Informed consent not completed correctly.
- Non-compliance with study treatment.
- Prohibited medications/procedure.
- Visit/procedure missing or out of window.
- The Endo study team will approve all final protocol deviation assignments and classify them as either major or minor during ongoing protocol deviation review meetings, with the final meeting held prior to the database lock.

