5. ANALYSIS POPULATIONS

The study will use the following analysis populations for data summarization.

Table 11: Analysis Population

Population	Definition	Displays
Safety Population	The Safety Population will include all subjects who have undergone any MRI or biopsy at Screening.	All demographic and baseline characteristics as well as safety parameters will be summarized based on this population.
Evaluable Population	The Evaluable Population will include all subjects in the Safety Population who have a baseline and at least 1 post-injection PR-PCSS evaluation.	All efficacy analyses will be based on this population.

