7.6.1. Primary Endpoint

7.6.1.1. Change from Baseline in PR-PCSS Rating at Day 71

The baseline PR-PCSS ratings and the level of change in PR-PCSS ratings from Baseline (Screening) at Day 71 will be summarized using frequency counts and percentages for each severity rating and with mean and SD.

To assess the impact of CCH at Day 71, the PR-PCSS ratings at Day 71 will be compared with Baseline ratings using paired *t* test. The normality assumption of the difference of assessment will be evaluated using Shapiro-Wilk test and Q-Q plot.

Two-sided *p* value with 5% level of significance will be used to check if normality is achieved or not. Normality will be concluded if the *p* value > 0.05.

In case normality assumption is not met then Wilcoxon Signed Rank Pratt Lehmann test (adjusted for the correction factor for ties and zeros, if present) will be used.

The result of the analysis will be presented as:

SAS appendix will be presented detailing the test of normality of differences in Day 71 and Baseline PR-PCSS ratings.

Paired *t* test: Mean difference between Baseline and Day 71 ratings and associated 95% CI, SE, and *p* value. The negative mean difference indicates improvement in cellulite severity at Day 71.

Wilcoxon Signed Rank Pratt Lehmann test: Sum of positive ranks, sum of negative ranks and *p* value will be presented. If the sum of the negative rank is greater than the sum of positive rank, then it indicates improvement in cellulite severity at Day 71.

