8. CHANGE FROM PROTOCOL

This SAP is prepared primarily based on the study protocol; original version dated October 22, 2019 and protocol amendment 1 dated January 16, 2020.

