9. REVISION HISTORY

This SAP is the first version.

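### The SAP's Evaluable Population omits the protocol's first-dose-after-18-March-2020 condition, so up to 7 COVID-interrupted subjects could enter the efficacy analyses

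*SAP*

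**What the plan says.** The SAP (section 5, Table 11) defines the efficacy set as follows: "The Evaluable Population will include all subjects in the Safety Population who have a baseline and at least 1 post-injection PR-PCSS evaluation". It assigns all efficacy analyses to that set. Section 7.6 tabulates efficacy by side and by region, and for the primary endpoint section 7.6.1.1 says "the PR-PCSS ratings at Day 71 will be compared with Baseline ratings using paired" *t* test, with a signed-rank test as fallback.

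Protocol section 9.2 has the same structure but restricts the set to those "who received their first dose of CCH in this study after 18 March 2020 and who had a baseline" and a later PR-PCSS rating. Sections 1.1, 2.1 and 4.1 agree: subjects dosed before the suspension count for safety only, and "all efficacy assessments will be based on the data from these 12 subjects", meaning the 12 additional subjects.

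On who was dosed early, protocol section 2.1 reports 7 subjects at suspension: "Of those 7 subjects, 2 had completed the 3 doses required for the study and 1 subject had completed 2 doses".

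The SAP says which protocol it follows. Section 8 names the "original version dated October 22, 2019 and protocol amendment 1 dated January 16, 2020", and section 9 says "This SAP is the first version". The supplied protocol is Amendment 3.

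**The concern.** The condition that separates the two groups of subjects is in one governing document and missing from the other. A programmer working from Table 11 would build the efficacy set without regard to the date of first dose.

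The earlier subjects differ from the new ones in ways that bear on the primary endpoint. Five had incomplete dosing when the site closed, so any later doses came after an interruption. The other two had all three doses. By 15 April 2020, however, all 7 were more than a week outside the window for their next dose or Day 71 visit, so a Day 71 rating obtained after re-opening would be late. If any of the 7 has such a rating, the primary result under the SAP is not the result the protocol defines.

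The study is small and reported by region, so even one extra subject carries weight: 1 of 7 (14%) in a region with 6 new subjects.

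**Working it through.** **Inputs**
- New subjects: 12 (protocol 4.1). Dosed before suspension: 7 (protocol 2.1). Planned total: about 19 (protocol 4.1).
- Doses at suspension: 2 subjects with three and 1 with two (protocol 2.1).
- PR-PCSS visits: Screening and Days 22, 43, 71, 161 and 251 (SAP 4.5). On treatment days assessments come before dosing (schedule of activities, closing note).
- No subject had completed all Day 71 assessments at suspension (protocol 2.1). Continuing was voluntary (protocol 4.1).

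**Plan's own figure.** 12 + 7 = 19, which reproduces the stated total.

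**Dose breakdown.** 7 − 2 − 1 = 4 subjects with one dose.

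**Who meets the SAP definition?** A subject with at least two doses has passed the Day 22 visit, where a rating was due before injection. By schedule, 2 + 1 = 3 earlier subjects already qualify. The 4 one-dose subjects qualify only if they returned and gave a rating. Assuming all 12 new subjects are evaluable:
- 3 by schedule: 3/(12 + 3) = 3/15 = 20.0%
- all 7: 7/(12 + 7) = 7/19 = 36.8%
- under protocol 9.2: 0/12

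**Who enters the Day 71 test?** It also needs a Day 71 rating, so 0 to 7 earlier subjects. The SAP schedule allows Day 71 to run up to 10 days late. A later rating falls under the deviation type "Visit/procedure missing or out of window" (SAP 4.2), but no SAP rule drops it from analysis.

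**Illustration of the effect on the Day 71 mean.** The documents give no response figures, so this is an assumption. Suppose the 5 subjects with incomplete dosing at suspension show a fraction *f* of the full-course change, and the 2 three-dose subjects show all of it. Ratio of pooled to intended mean:

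| Earlier subjects with a Day 71 rating | Formula | *f* = 0.3 | *f* = 0.5 | *f* = 0.7 |
|---|---|---|---|---|
| none | 12/12 | 1.000 | 1.000 | 1.000 |
| the 3 with at least two doses | (14 + *f*)/15 | 0.953 | 0.967 | 0.980 |
| all 7 | (14 + 5*f*)/19 | 0.816 | 0.868 | 0.921 |

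**By region.** The regional split of the 7 is not given. With 6 new subjects and *j* earlier ones in a region, the share is *j*/(6 + *j*), from 0 to 7/13 = 53.8%. At *j* = 7 the mean ratio is (8 + 5*f*)/13 = 0.731, 0.808 and 0.885.

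**Search for another safeguard.** SAP sections 3 to 7 contain no other date condition or exclusion that would remove the 7. SAP 6.3 instead says that available data from subjects who discontinue will be summarised.

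**The case against.** The strongest reply is that this is a version mismatch. The SAP follows Amendment 1, dated before the suspension, so the condition could not have been in it. Protocol 9.3 promises a detailed SAP before the interim analysis, and a later one may exist. That explains the omission but does not cure it: the only SAP supplied calls itself the first version, and it has no rule that the protocol prevails.

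Second, the effect on the primary endpoint is conditional and could be nil. This stands. The study also has no formal sample size, and the protocol plans only descriptive summaries. The SAP, however, specifies two-sided tests at 0.05 with a p value and confidence interval.

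Third, the exposure that does not depend on return is not shown to cause bias. The three subjects' Day 22 ratings, and the three-dose subjects' Day 43 ratings, were due before the interruption and after the same number of doses as in new subjects. This also stands. Including them breaches the protocol's population, but there is no evidence that it distorts the estimate.

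Fourth, the values of *f* have no basis in the documents, and the 5 may have received their remaining doses. The 7-of-13 case gives the largest share, not the lowest mean: the 5 alone with 6 new subjects give (6 + 5*f*)/11 = 0.682, 0.773 and 0.864. The dilution figures are therefore illustrations only. The counts do not depend on them.

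**Conclusion.** The concern holds, and the text must be corrected before analysis. Followed as written, the SAP builds an efficacy set that the protocol rules out.

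The firm part is the count: at least 3 of the 7 earlier subjects qualify if their scheduled Day 22 ratings were done, and all 7 could. The Day 22 and Day 43 secondary analyses are exposed even if nobody returned. The Day 71 primary analysis is exposed only to the extent that earlier subjects came back and were rated.

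The size of any shift in the Day 71 mean cannot be known from the documents. Under the stated assumption it runs from no change to a pooled mean 82% of the intended value when *f* = 0.3 and all 7 are included, with larger shifts possible within one region. The population conflict itself needs no such assumption.

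**What to change.** In SAP Table 11, add to the Evaluable Population the protocol 9.2 condition that the first CCH dose in this study came after 18 March 2020. List the earlier subjects' efficacy data apart from the efficacy analyses. Keep the separate interim assessment of MRI and biopsy data from the three-dose subjects (protocol 9.4).

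Then align the rest of the SAP with Amendment 3:
- 3.1 and 3.3: number dosed
- 4.1 and 6.3: completion and replacement
- 6.4: interim trigger, now all subjects at Day 71, against at least 4 of the 12 new subjects in protocol 9.4; the protocol also adds tertiary endpoints
- 8: protocol version
- 7.8: MRI and biopsy summaries use the Safety Population, where protocol 9.3.2 uses the Evaluable Population; the Table 11 change alone would not reach these tables
- Table 11, Safety Population: any screening MRI or biopsy, against the screening biopsy in protocol 9.2; this does not alter the count of 7

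The population change costs one sentence and one programmed date flag. The alignment is SAP wording, with matching changes to the outputs it governs. Neither needs new data or patients.

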6. STATISTICAL METHODS

6.1. General Methodology

All statistical analysis, summary tables and data listings will be prepared using version 9.3 or later of SAS® software.

All statistical tests of efficacy parameters will be 2-sided with a significance level of $\alpha=0.05$, unless specified otherwise.

Continuous data will be summarized using descriptive statistics (number of subjects [n], mean, standard deviation [SD] or standard error [SE], median, minimum [min], and maximum [max]) and discrete data will be summarized using frequency counts and percentages, the denominator will be based on the number of subjects in the appropriate population. For the purpose of display, the summary results will be rounded as follows:

- Min and max: same number of decimal places as the raw data.
- Mean and median: 1 more decimal place than the raw data.
- SD/SE: 2 more decimal places than the raw data.
- Percentages will be displayed with 1 decimal precision. A zero count will not have the associated percentage presented on the table (ie, no 0%).
- The standard form of a percentage change variable is 0 decimal places.

For categorical variables with missing values, a category documenting the frequency of missing values will be displayed in the summary tables.

Summary tables, subject listings and any supportive SAS output will include a “footer” of explanatory notes that will indicate, when applicable:

- Date of data extraction
- Date and time of output generation
- SAS program name, including the path, that generates the output

When calculating percentages, the denominator will be based on the number of subjects with non-missing values. If the denominator is expected to change over time, then the denominator used to calculate the percentage should be based on the number of subjects with non-missing values at each visit. Any subject removed from an analysis will be noted at the bottom of the table along with the reason the subject was removed.

Null summary tables will be presented with a note stating that “No Subjects Met Criteria”.

Subject listings of all data from the eCRFs as well as any derived variables will be presented.

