9.3.1. Efficacy Analysis

The primary endpoint of change from baseline in PR-PCSS at Day 71 will be summarized by treatment area (left or right) and region (buttock or thigh) using appropriate descriptive statistics using the Evaluable Population.

All secondary and tertiary PR-PCSS, CR-PCSS, and Hexsel efficacy endpoints will be summarized by treatment area (left or right) and region (buttock or thigh) using appropriate descriptive statistics using the Evaluable Population.

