7.6.2. Secondary Endpoints

7.6.2.1. Change from Baseline in PR-PCSS Rating at Days 22 and 43

The baseline PR-PCSS ratings and the level of change in PR-PCSS ratings from Baseline (Screening) at Day 22 and 43 will be summarized using frequency counts and percentages for each severity rating and with mean and SD.

In addition, the PR-PCSS ratings at Day 22 and 43 will be compared with Baseline ratings using similar analysis as mentioned for primary endpoint. Refer to Section 7.6.1.1 for more details.

7.6.2.2. Change from Baseline in CR-PCSS Rating at Days 22, 43, and 71

The baseline CR-PCSS ratings and the level of change in CR-PCSS ratings from Baseline (Screening) at Days 22, 43, and 71 will be summarized using frequency counts and percentages for each severity rating and with mean and SD.

In addition, the CR-PCSS ratings at Days 22, 43, and 71 will be compared with Baseline ratings using similar analysis as mentioned for primary endpoint. Refer to Section 7.6.1.1 for more details.

7.6.2.3. Changes in the Hexsel CSS Total Score from Baseline at Days 22, 43, and 71

The baseline Hexsel CSS scores and the level of change in Hexsel CSS scores from Baseline (Screening) at Days 22, 43, and 71 will be summarized using frequency counts and percentages for each severity scores and with mean and SD.

In addition, the Hexsel CSS total score ratings at Days 22, 43, and 71 will be compared with Baseline using similar analysis as mentioned for the primary endpoint. Refer to Section [7.6.1.1](#) for more details.

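### The SAP adds unadjusted 0.05 tests to endpoints that the protocol only describes, and does not say which test decides the primary endpoint

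*SAP*

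**What the plan says.** **Protocol 9.3.1** handles the primary endpoint by summary: "The primary endpoint of change from baseline in PR-PCSS at Day 71 will be summarized by treatment area (left or right) and region". The same paragraph gives the method as "using appropriate descriptive statistics using the Evaluable Population". The next paragraph treats the secondary and tertiary rating endpoints the same way. No test is named. Protocol 9.1 states that no formal sample size calculation was made.

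**SAP 6.1** says "All statistical tests of efficacy parameters will be 2-sided with a significance level of" 0.05 unless otherwise specified. SAP 7.6.1.1 then states that "the PR-PCSS ratings at Day 71 will be compared with Baseline ratings using paired" *t* test, with a signed-rank (Pratt-Lehmann) test if Shapiro-Wilk rejects normality. SAP 7.6.2 carries this over to the secondary endpoints. For example, "the PR-PCSS ratings at Day 22 and 43 will be compared with Baseline ratings using similar analysis as mentioned for primary endpoint". CR-PCSS and the Hexsel total are treated likewise at Days 22, 43 and 71.

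**Unit of analysis.** The opening of SAP 7.6 presents efficacy by side and by region. SAP 4.5.1 to 4.5.4 define each change for the treatment region, meaning both buttocks or both thighs. The paragraphs that describe the tests name neither.

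**SAP 8**, headed as changes from the protocol, opens "This SAP is prepared primarily based on the study protocol" and lists the original protocol and amendment 1. It does not mention the tests.

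**The concern.** A level of 0.05 attached to every efficacy test invites the reader to call any result below it significant. Nothing in either document says which p-value answers the primary question, or whether the two regions (and perhaps the two sides) are to be read together or separately. That choice would then be made after the results are known.

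The study is open-label, has no control arm and plans 12 evaluable women. A significant change from baseline is easily over-read as a drug effect, and more so when it can be picked from several cells. What is at stake is the wording of the report's efficacy claims.

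**Working it through.** **Inputs**
- Per-test level: 0.05, two-sided (SAP 6.1).
- Endpoint-visits tested: PR-PCSS at Day 71 (SAP 7.6.1.1) and Days 22 and 43 (7.6.2.1); CR-PCSS at three visits (7.6.2.2); Hexsel total at three visits (7.6.2.3). The tertiary endpoints (7.6.3) get counts and percentages only, so no tests.
- Women: 6 treated in the buttocks and 6 in the thighs, none in both (SAP 3.3). The regions are therefore independent samples.
- Not given, so assumed below: correlations between sides, scales and visits, and the distribution of rating changes.

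**Step 1. The stated level.** For one test, 1 − 0.95 = 0.05. The SAP's figure holds as a per-test level.

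**Step 2. Count.** Endpoint-visits: 1 + 2 + 3 + 3 = 9.
- By region (SAP 4.5.1 to 4.5.4): 9 × 2 = 18 tests, 2 of them primary.
- By side and region (opening of SAP 7.6): 9 × 4 = 36 tests, 4 of them primary.

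**Step 3. Primary endpoint, chance of at least one false positive if each test has size 0.05**
- Two regions, one value per woman: 1 − 0.95² = 0.0975. No correlation assumption is needed, because the women differ.
- Four independent cells: 1 − 0.95⁴ = 0.1855. If the two sides of a woman were perfectly correlated, this falls back to 0.0975.

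**Step 4. All tests.** If independent, 1 − 0.95¹⁸ = 0.603 with 18 × 0.05 = 0.9 false positives expected, or 1 − 0.95³⁶ = 0.842 with 36 × 0.05 = 1.8 expected. Independence is unrealistic within a woman. Simulated paired *t* tests on continuous data, 6 women per region, equal pairwise correlation within a woman:

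| Assumed correlation | Any of 4 primary | Any of 36 |
|---|---|---|
| 0 | 18.3% | 83.9% |
| 0.5 | 18.0% | 69.4% |
| 0.7 | 16.6% | 55.0% |
| 0.9 | 14.4% | 32.9% |

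If the correlation instead multiplies across side, scale and visit, values of 0.5, 0.7 and 0.9 give 17.9%, 16.7% and 14.1% for the primary cells, and 76.5%, 64.7% and 39.7% for all 36. The primary figure barely depends on the structure; the overall figure does.

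**Step 5. Is the true size 0.05?** PR-PCSS moves in whole steps from 0 to 4. Applying the SAP's Shapiro-Wilk switch to 6 women, with a normal approximation for the rank test, under three assumed symmetric no-effect distributions:
- changes of −1, 0, +1 with probabilities 0.25, 0.5, 0.25: size 0.0356; four independent cells 1 − 0.9644⁴ = 0.135;
- the same steps with 0.1, 0.8, 0.1: size 0.002; four cells 1 − 0.998⁴ = 0.008;
- changes of −2 to +2 with 0.1, 0.2, 0.4, 0.2, 0.1: size 0.052; four cells 1 − 0.948⁴ = 0.192.

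If ratings rarely change under no effect, the inflation can disappear. These sizes are for a single side; the mean of two sides takes half-point values, so they do not carry over directly.

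**Step 6. Interim.** SAP 6.4 places the interim after all Day 71 visits, when the Day 22 to 71 data are complete, so the tests are not repeated on growing data. Protocol 9.4 places it when at least 4 of the 12 new women have reached Day 71. Only there would the SAP's tests be run twice.

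**The case against.** The case for leaving the SAP alone has real force.

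- **0.05 is a per-test level.** A reader might infer that the SAP promises an error rate it does not deliver. It does not: neither document claims family-wise control. This stands in full.
- **The count of 36 is not stated.** A reader might take 36 tests and an 84% chance of a false positive as the plan's own position. The endpoint definitions support 18 equally well, 84% needs independence, and all but the 2 or 4 primary tests are labelled secondary. This stands. But both readings leave more than one primary test, and neither document describes a single pooled one.
- **No success rule is written.** A reader might infer that the primary endpoint is met if any cell falls below 0.05. The documents set no such criterion. The gap is that they set none at all.
- **Interim repetition.** A reader might infer a second round of tests. Under the SAP's own timing there is none, and the interim's only stated decision concerns MRI and biopsy.
- **The omission in SAP 8.** A reader might infer a silent departure from the protocol. Protocol 9.3 calls itself a general summary, the SAP was written from amendment 1, and the amendment 3 summary says 9.3.1 was then updated on descriptive statistics for secondary and tertiary ratings. The amendment 1 wording is not available, so the mismatch can be asserted only against the current protocol.
- **Exploratory study.** Protocol 2.1 treats efficacy as already shown elsewhere, and no decision is tied to these p-values. That lowers the stakes. It is also the reason to drop the significance level.

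**Conclusion.** The point holds in a limited form. The SAP adds 18 or 36 unadjusted tests to endpoints that the current protocol only describes, and it does not identify the test that decides the primary endpoint. The chance of at least one false positive there is 9.75% by region, or between 9.75% and about 18.5% by side and region depending on how alike a woman's two sides are. Both figures assume a true size of 0.05 per test and, by region, one value per woman. With whole-step ratings and six women per region the true figure may be well below these, or marginally above (19.2% in one assumed case).

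The documents do not support saying that the stated level is false, or that the interim doubles the testing. The defect is an undefined primary test and p-values whose status is not stated.

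**What to change.** 1. In SAP 6.1, replace the significance-level sentence with a statement that all p-values are nominal and that no claim of significance is made.
2. In SAP 7.6, report mean change with 95% CI for every endpoint-visit. At present the CI comes only with the *t* test; the signed-rank branch gives rank sums and a p-value.
3. If one test is kept, name it: Day 71 PR-PCSS, one value per woman (mean of her two sides), all evaluable women together, at the final analysis only, two-sided 0.05. Label every other p-value nominal. This pools the buttock and thigh versions of the scale, both rated 0 to 4; the summaries by side and region stay as description.
4. Record the added testing in SAP section 8.

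A Bonferroni split is not a workable alternative. The levels would be 0.05/2 = 0.025 or 0.05/4 = 0.0125, while an exact signed-rank test on six women cannot give a two-sided p below 2/2⁶ = 0.031.

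Cost: SAP wording and the matching table layouts, with no new data. No result other than the one named test, if it is kept, could be called significant.
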